### **9.3.4. Worsening Laboratory Events of Special Interest**

Laboratory events of special interest are listed below.

- ALT increased
- AST increased
- Absolute neutrophil count decreased

The time to onset of a worsening laboratory event is defined as the interval between the date of first dose of study drug and the date of the first occurrence of CTC grade worse than baseline for the laboratory event. Participants who have not experienced a worsening laboratory event at the time of analysis will be right-censored at the last postbaseline study visit with nonmissing CTC grade of the laboratory event.

Time to onset of worsening Grade 3 or 4 laboratory events of special interest will be summarized using descriptive statistics and the life-table method as described in Section 9.2.2, and the Kaplan-Meier plot of time to onset of worsening Grade 3 or 4 absolute neutrophil count decreased will be provided. Laboratory events of special interest to be summarized may be adjusted based on emerging data.

## **9.4. Vital Signs**

Values at each scheduled visit, change, and percent change from baseline for vital signs, including systolic blood pressure, diastolic blood pressure, pulse, body temperature, respiratory rate, and weight will be summarized descriptively.

Normal ranges for vital sign values are defined in Table 4. The abnormal values for participants exhibiting vital sign abnormalities will be listed along with their assigned treatment regimen. Alert vital signs are defined as an absolute value outside the defined range and percentage change greater than 25%. Note that the definition of alert vital signs does not apply for body temperature and weight. The abnormal values for participants exhibiting alert vital sign abnormalities will be listed.

**Table 4: Normal Ranges for Vital Sign Values**

Parameter	High Threshold	Low Threshold
Systolic blood pressure	≤ 155 mmHg	≥ 85 mmHg
Diastolic blood pressure	≤ 100 mmHg	≥ 40 mmHg
Pulse	≤ 100 bpm	≥ 45 bpm
Temperature	≤ 38°C	≥ 35°C
Respiratory rate	≤ 24 breaths/min	≥ 12 breaths/min

### 9.5. Electrocardiograms

Twelve-lead ECGs including PR, QRS, QT, QTcB, QTcF, and RR intervals will be obtained for each participant during the study. Values at each scheduled visit, change, and percent change from baseline will be summarized for each ECG parameter. Baseline will be determined as the average of all nonmissing values before the first administration of INCB050465.

Normal ranges for ECG values are defined in Table 5. Electrocardiogram values will also be considered abnormal if the absolute percentage change from baseline is more than 25% (30% for QRS interval). Participants exhibiting ECG abnormalities will be listed with study visit and assigned treatment regimen. Abnormal values for participants with alert ECG values, defined as both the absolute value and the percentage change from baseline being outside normal ranges, will be identified and listed. Outliers of QT, QTcB, and QTcF values, defined as absolute values > 450 milliseconds or change from baseline > 30 milliseconds, will be summarized.

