11. Use or expected use during the study of any prohibited medications, including potent CYP3A4 inhibitors or inducers (see [Appendix D](#)), within 14 days or 5 half-lives (whichever is longer) before the date of study treatment administration.
12. Significant concurrent, uncontrolled medical condition, including, but not limited to, renal, hepatic, hematological, GI, endocrine, pulmonary, neurological, cerebral, or psychiatric disease.
13. Current or previous other malignancy within 3 years of study entry, except cured basal or squamous cell skin cancer, superficial bladder cancer, prostate intraepithelial neoplasm, carcinoma *in situ* of the cervix, or other noninvasive or indolent malignancy without sponsor approval.
14. History of stroke or intracranial hemorrhage within 6 months of the date of study treatment administration.
15. Chronic or current active infectious disease requiring systemic antibiotics, antifungal, or antiviral treatment or exposure to a live vaccine within 30 days of dosing.
16. Known HIV infection or positivity on immunoassay. **Note:** HIV screening test is optional for subjects enrolled in the United States, but subjects with known HIV infection in the United States will be excluded.
17. Liver disease: HBV or HCV infection: Subjects positive for HBsAg or hepatitis B core antibody will be eligible if they are negative for HBV-DNA; these subjects should be considered for prophylactic antiviral therapy. Subjects positive for anti-HCV antibody will be eligible if they are negative for HCV-RNA.
18. Clinically significant cardiac disease, including unstable angina, acute myocardial infarction, and/or cardiac conduction issues within 6 months of the date of study treatment administration.
19. Current New York Heart Association Class II to IV congestive heart failure or uncontrolled arrhythmia.
20. Presence of an abnormal ECG that is clinically meaningful. Screening QTc interval > 450 milliseconds is excluded (corrected by Fridericia). In the event that a single QTc is > 450 milliseconds, the subject may enroll if the average QTc for 3 ECGs is < 450 milliseconds.
21. Unable to swallow and retain oral medication, malabsorption syndrome, disease significantly affecting GI function, total resection of the stomach or small bowel, ulcerative colitis, symptomatic inflammatory bowel disease, or partial or complete bowel obstruction.
22. Known hypersensitivity or severe reaction to INCB050465 or its excipients (see [IB](#)).

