7.5.5. Electrocardiograms

All 12-lead ECGs will be performed with the subject in a recumbent or semirecumbent position after 5 minutes of rest. The 12-lead ECGs will be performed locally and be interpreted by the investigator at the site and used for immediate subject management. Baseline ECGs obtained during screening can be performed using a single measurement; however, ECGs may be performed in triplicate if the single QTc measurement is > 450 milliseconds (corrected by Fridericia; see Section 3.2). The decision to include or exclude a subject or discontinue a subject's participation in the study based on an ECG flagged as "Abnormal, Clinically Significant" is the responsibility of the investigator, in consultation with the sponsor's medical monitor, as appropriate. If a single measurement demonstrates a QTc interval > 500 milliseconds, 2 more ECGs should be obtained over a brief period, and the averaged QTc intervals should be used to determine whether the study treatment should be interrupted (see Section 5.4.1).

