**Table 5: Normal Ranges for Electrocardiogram Values**

Parameter	High Threshold	Low Threshold
PR	≤ 220 msec	≥ 75 msec
QRS	≤ 120 msec	≥ 50 msec
QT	≤ 500 msec	≥ 300 msec
QTcF, QTcB	≤ 450 msec	≥ 295 msec
RR	≤ 1330 msec	≥ 600 msec

QTcF = Fridericia's correction; QTcB = Bazett's correction.

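### The SAP 9.5 alert rule can leave a QTcF above 500 ms off the ECG alert listing when the baseline is above 400 ms

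*SAP*

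**What the plan says.** SAP 9.5 sets up three ways of flagging an ECG value.

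- **Abnormal.** The value lies outside the limits in SAP Table 5, "Normal Ranges for Electrocardiogram Values", where the upper limit for QTcF and QTcB is 450 ms. A value can also qualify on relative change alone: "Electrocardiogram values will also be considered abnormal if the absolute percentage change from baseline is more than 25% (30% for QRS interval"). Abnormal values go to Listing 2.10.2.
- **Alert.** Both conditions must hold: "alert ECG values, defined as both the absolute value and the percentage change from baseline being outside normal ranges". Alert values go to Listing 2.10.3.
- **Outlier.** "Outliers of QT, QTcB, and QTcF values, defined as absolute values > 450 milliseconds or change from baseline > 30 milliseconds, will be summarized". This feeds Table 3.5.8.

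The reference point for change is also given in SAP 9.5: "Baseline will be determined as the average of all nonmissing values before the first administration of INCB050465".

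Two Protocol provisions bear on the alert rule. Exclusion criterion 20 limits entry: "Screening QTc interval > 450 milliseconds is excluded (corrected by Fridericia"), with entry still possible after a single higher reading if three ECGs average below 450 ms. Protocol 7.5.5 sets a response for on-study readings: "If a single measurement demonstrates a QTc interval > 500 milliseconds, 2 more ECGs should be obtained over a brief period". The averaged QTc then informs whether treatment is interrupted.

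**The concern.** An alert listing is where a reader looks first for the readings that matter most. For QTc, the Protocol itself says which single reading calls for a response: one above 500 ms. The alert rule does not refer to that level. It adds a relative-change condition to the 450 ms limit, and for a parameter whose baseline can be as high as 450 ms, a 25% change is a very large shift. The rule can therefore pass over readings above the Protocol's own trigger, most easily in subjects who start with the longest QTcF.

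ECGs are part of the secondary safety endpoint (Protocol Table 1; SAP Table 1). At stake is whether Listing 2.10.3, read by itself, gives a fair picture of the most prolonged QTcF values.

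**Working it through.** The plan states no figure on this point, so there is nothing to reproduce. The check applies the SAP rule directly.

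**Inputs**

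- Upper QTcF limit: 450 ms (SAP Table 5).
- Relative-change limit for QTcF: more than 25% (SAP 9.5). The alert sentence does not repeat the 25%, but it is the only percentage limit given for QTcF; the 30% limit is for QRS.
- Level for repeat ECGs: a single QTc above 500 ms (Protocol 7.5.5).
- Top of the baseline range considered: 450 ms (Protocol 3.2, criterion 20).

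**Formula.** For a prolongation from baseline B, an alert needs QTcF > 450 and QTcF > 1.25 × B. The cut-off is therefore max(450, 1.25 × B). The percentage condition takes over once 1.25 × B > 450, that is B > 360 ms. The cut-off passes 500 ms once B > 500/1.25 = 400 ms.

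**A reading of 501 ms.** The break-even baseline is 501/1.25 = 400.8 ms. In whole milliseconds:

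- B = 400: 101/400 = 25.25%, alert.
- B = 401: 100/401 = 24.94%, not an alert.
- B = 420: 81/420 = 19.29%, not an alert.
- B = 450: 51/450 = 11.33%, not an alert.

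Every whole-number baseline from 401 to 450 ms gives no QTcF alert.

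**Cut-off by baseline.** The last column is the width of the band of readings above 500 ms that are not QTcF alerts, 1.25 × B − 500.

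| Baseline (ms) | Alert cut-off (ms) | Rise to reach cut-off (ms) | Band above 500 ms not flagged (ms) |
|---|---|---|---|
| 360 | 450 | 90 | none |
| 380 | 475 | 95 | none |
| 400 | 500 | 100 | 0 |
| 401 | 501.25 | 100.25 | 1.25 |
| 410 | 512.5 | 102.5 | 12.5 |
| 420 | 525 | 105 | 25 |
| 440 | 550 | 110 | 50 |
| 450 | 562.5 | 112.5 | 62.5 |

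**Two cases side by side.** From 360 to 451 ms is a rise of 91 ms, or 25.3%: an alert. From 420 to 520 ms is a rise of 100 ms, or 23.8%: not an alert, although both the rise and the final value are larger.

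**Other outputs.** At each baseline from 401 to 450 ms, a 501 ms reading is above 450 ms and has risen by 51 to 100 ms. It is therefore abnormal (Listing 2.10.2) and meets both outlier criteria for Table 3.5.8. The outlier definition, however, does not separate 501 ms from, say, 455 ms. The only 500 ms limit in SAP Table 5 and Protocol Table 11 is for uncorrected QT.

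**The case against.** **The listing is an extra.** Protocol 9.4.2.4 asks only that clinically notable ECGs, including QTcF above 450 ms, be listed, and Listing 2.10.2 does this with no percentage condition. The Protocol defines no ECG alert; it uses that term for vital signs, with a similar range-plus-25% rule. The SAP rule is complete and reproducible, and nothing obliges it to mirror the 7.5.5 trigger. This stands in part. A reader might infer a conflict between Protocol and SAP, and the documents do not support that. What remains is that a better rule is available at almost no cost.

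**The readings are not lost.** This stands. They are in Listing 2.10.1 (all values) and Listing 2.10.2, and they meet the outlier definition. SAP 9.5 also promises by-visit summaries ("Values at each scheduled visit, change, and percent change from baseline will be summarized for each ECG parameter"), and SAP 5.1 includes the maximum among the descriptive statistics. A maximum above 500 ms at a scheduled visit would therefore show, though not the number of subjects or any unscheduled ECG. A reading that requires a change in study drug is also an AE under Protocol 8.1.1, and the same ECG may be an alert through another parameter. With about 90 subjects, cases could be counted by hand from the listings.

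**A count above 500 ms may already be planned.** A reader might infer that the trial will produce no such count. The documents do not support that either. Table 3.5.8 is marked as a standard table, and its layout is held in a shell outside the documents. Table 3.5.9 summarizes clinically significant ECG abnormalities, and a reading that prompts repeats could well be flagged as one. That flag rests on investigator judgment, so Table 3.5.9 is not a defined count above 500 ms. The supportable statement is only that the text of SAP 9.5 names no such category.

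**One reading is not an interruption.** This stands. Protocol 7.5.5 uses a single value above 500 ms to trigger repeats and uses the average for the decision. It gives no numeric interruption threshold there, and a single 501 ms reading may average lower.

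**Bazett values.** The screening and clinically notable QTc limits in the Protocol are Fridericia-corrected, and the argument here is about QTcF. It does not justify a matching change for QTcB.

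**Conclusion.** The point holds as a minor weakness in safety reporting. The QTcF alert cut-off rises with baseline and exceeds 500 ms for any baseline above 400 ms. The band of readings above 500 ms that are not QTcF alerts grows to 62.5 ms at a baseline of 450 ms. Someone relying on Listing 2.10.3 alone could miss a reading above the Protocol's repeat-ECG level while seeing a smaller rise to a lower value.

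This rests on three assumptions: that 25% is the percentage limit meant in the alert sentence, that the QTc in Protocol 7.5.5 is Fridericia-corrected as elsewhere in the Protocol, and that 450 ms is taken as the top of the baseline range. The documents give no baseline QTcF distribution and no QTc event rate, so the number of readings affected is unknown and may be zero.

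A reader might go further and infer a risk to subjects. The documents do not support that: sites act on local ECGs under Protocol 7.5.5, independently of the alert listing. Efficacy analyses are untouched.

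**What to change.** Add one sentence to SAP 9.5: *Any postbaseline QTcF > 500 milliseconds is an alert value regardless of percentage change from baseline.* With this, 501 ms is an alert from every baseline up to 450 ms.

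In Table 3.5.8, report subjects with QTcF above 450 ms and above 500 ms in separate rows. If the standard shell already does so, a statement to that effect in SAP 9.5 is enough.

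The cost is one sentence and at most one table row, using data already collected. The downside is a slightly longer alert listing.

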**Table 5: Normal Ranges for Electrocardiogram Values**

Parameter	High Threshold	Low Threshold
PR	≤ 220 msec	≥ 75 msec
QRS	≤ 120 msec	≥ 50 msec
QT	≤ 500 msec	≥ 300 msec
QTcF, QTcB	≤ 450 msec	≥ 295 msec
RR	≤ 1330 msec	≥ 600 msec

QTcF = Fridericia's correction; QTcB = Bazett's correction.

## **10. INTERIM ANALYSES**

An interim futility analysis is planned for Cohort 2 when 30 participants have been treated and evaluated for response or have permanently discontinued study treatment because of disease progression, withdrawal of consent, or death.

Cohort 2 will be terminated for futility if  $\leq 10$  of the 30 participants responded (ie, CR or PR) based on assessments provided by IRC; otherwise, the study for Cohort 2 will continue. The probability of stopping at interim for futility is 0.29 when the true response rate is 40%, 0.05 when the true response rate is 50%, or 0.003 when the true response rate is 60%.

An IDMC will be charged with evaluating interim futility results. The IDMC will consist of clinicians and an independent statistician. The IDMC will make recommendations to the sponsor at the planned interim futility analysis for Cohort 2. The process by which the IDMC will make recommendations and decisions will be documented in the IDMC Charter. Additional operational details of the interim analyses, including tables, figures, and listings provided to the IDMC, will be provided in the IDMC Charter.

## 11. CHANGES AND MODIFICATIONS TO THE ANALYSIS PLAN

All versions of the SAP are listed in [Table 6](#).

**Table 6: Statistical Analysis Plan Versions**

SAP Version	Date
Original	21 FEB 2019
Amendment 1	27 AUG 2020
Amendment 2	28 JAN 2021

### 11.1. Changes to Protocol-Defined Analyses

Not applicable.

### 11.2. Changes to the Statistical Analysis Plan

#### Amendment 2 (28 JAN 2021)

**Overall Rationale for the Amendment:** The primary purpose of this amendment is to comply with responses to comments provided by FDA regarding the Statistical Analysis Plan Amendment 1.

- Section [6.4](#) was updated to include the summary for the number of dose reductions and the number of dose interruptions of each participant.
- Section [7.3](#) was updated to include the timing of primary efficacy analysis.
- Section [7.3.1](#) was updated to include a sensitivity analysis of ORR that summarizes participants who switched to the selected dose after starting the maintenance dose in a separate treatment regimen and to include an additional analysis on the number of participants who achieved best overall response after the time of crossover along with the best overall response data for this separate treatment regimen.
- Section [7.4.1](#) and Section [7.4.3](#) were updated to included sensitivity analyses where response assessments after the time of crossover will be excluded from the determination of DOR and PFS for participants who switched to the selected treatment regimen after starting the maintenance dose.
- Section [7.4.2](#) was updated to include a sensitivity analysis of CRR by summarizing participants who switched to the selected dose after starting the maintenance dose in a separate treatment regimen.
- Section [9.2.1](#) was modified to clarify how AEs that occur after new anti-lymphoma therapy will be assessed.
- **Incorporation of minor changes.** Other minor changes have been incorporated throughout the SAP and are noted in the redline version of the amendment.

### Amendment 1 (27 AUG 2020)

- Section 4.1.4 was updated to include details of rules for handling partial/missing onset or end date of TEAEs in the calculation of time to onset or duration of a TEAE. Rules for partial/missing date of last dose were updated to include details of handling situations where both month and day are missing.
- Section 5.2 was modified to provide details regarding how crossover participants will be summarized.
- Section 5.3 was updated to remove the efficacy evaluable analysis set and use the FAS for all analyses on efficacy data. This change is to comply with comments from FDA that any participants who received at least 1 dose should be included in the efficacy analyses for a single-arm trial. The all-screened population was added for the summary of analysis populations.
- Section 6.1.2 was modified to remove summaries of tumor markers but only keep listings. Relapsed/refractory status to the most recent prior therapy was added to the summary table of disease history because the response to last regimen before entering the study may be a prognostic factor for clinical outcomes.
- Section 6.2 was modified to add summaries of participants who are ongoing with treatment or still in the study.
- Section 6.4 was modified to change the calculations of duration of treatment and average dose during the maintenance dosing period because Group B with 2.5 mg QD was selected as the maintenance dose.
- Section 7.3 and Section 7.4 were modified to add efficacy analyses for participants in the FAS who have at least 2 prior therapies to support an indolent NHL indication in the same line of therapy as with follicular lymphoma in Study INCB 50465-203.
- Section 7.3.1 was modified to replace the efficacy evaluable analysis set with the FAS. This change is to align with Protocol Amendment 4 dated 23 DEC 2019 and include all treated participants in the efficacy analyses to comply with comments from FDA.
- Section 7.3.2 was modified to add "unknown" as a category for bone marrow involvement at baseline. Relapsed/refractory status to the most recent prior therapy was added to the subgroup analysis because the response to last regimen before entering the study may be a prognostic factor for clinical outcomes.
- Section 7.4.3 was modified to update references of censoring for PFS.
- Section 9.2.2 was updated to include details of analyses on time to onset of selected TEAEs of special interest. Summaries of longest duration of selected TEAEs of special interest were added to have a better understanding of the safety profile in terms of duration of class-effect AEs as well as AEs influenced by treatment regimens. "Grade 2 or higher" was changed to "Grade 3 or higher" for time to onset summary of rash. This change was made to be consistent with other PI3K inhibitors, which highlighted more severe cutaneous reactions graded as Grade 3 or higher in the labeling. "Herpes simplex virus infection" was changed to "herpes simplex" based on MedDRA coding dictionary

as a broader term. Exfoliative dermatitis was added to the list of TEAEs of special interest.

- Section 9.2.3 was updated to include summary of TEAEs by PT and maximum severity in decreasing order of frequency, summary of longest duration of selected TEAEs of special interest, and additional supporting summaries during the INCB050465 initial QD dosing period and the maintenance dosing period, which will provide supportive data of the safety profile of the maintenance dose. Summary of nonserious of TEAEs by SOC and PT was removed because it will not be used for the clinical study report but will be provided for result disclosure.
- Section 9.3.2 was modified to include ALT and AST in the line graphs as additional supportive analyses for laboratory events of special interest.
- Section 9.3.3 was added to identify potential Hy's law events to better monitor liver toxicity.
- Section 9.3.4 was updated to align with the analysis plan for adverse events of special interest. Summary of worsening of laboratory events of special interest was removed because this is covered by the summary of worsening of laboratory abnormalities.
- Section 9.5 was updated to change the high threshold of QTcF and QTcB interval from 460 to 450 milliseconds for purpose of analysis. This change is to comply with the categories outlined in FDA Guidance for Industry (E14 Clinical Evaluation of QT/QTc Interval Prolongation and Proarrhythmic Potential for Non-Antiarrhythmic Drugs) used to characterize outliers in QTc values.

## APPENDIX A. PLANNED TABLES, FIGURES, AND LISTINGS

This appendix provides a list of the planned tables, figures, and listings for the Clinical Study Report for Cohort 1 and Cohort 2. Outputs from Cohort 1 will have ".1" at the end of the numbering. Outputs from Cohort 2 will have ".2" at the end of the numbering. Shells are provided in a separate document for tables that are not in the Standard Safety Tables version 1.9.

The lists of tables, figures, and listings and the shells are to be used as guidelines. Modifications of the list that do not otherwise affect the nature of the analysis will not warrant an amendment to the SAP.

